1.2. Benefits and risks for research subjects

1.2.1. Benefits

1.2.1.1. *Individual profit*

Improved motor control
Improved practices with the use of non-slip socks

1.2.1.2. *Group profit*

Improved motor care for senior citizens, at a lower cost to society thanks to a shorter length of stay,
Improved motor management for faster discharge

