2.2.2. Secondary endpoints

1. Change in 10m walking speed between D1 (start of physiotherapy treatment) and D1' ("after a 3-minute walk with the shoe assigned following randomization"),
2. Evolution of isochrony between the speed of walking actually performed and the speed of walking imagined over 10m at D1, D1' and D8. The mean of two tests of each modality will be used.
3. Evolution of isochrony between walking speed and double-task walking speed over 10m at D1,D1' and D8 (Beauchet et al., 2010; Menant et al., 2014). The mean of two tests of each modality will be used.
4. Total score > 10 on the Short-Falls Efficacy Scale International questionnaire at D1, D1' and D8
5. Presence of fall(s) and their consequences during hospitalization
6. Length of stay calculated from start of hospitalization to end of hospitalization

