4.5.4. The presence of a fall

The occurrence of a fall during hospitalization, the time of the fall and its consequences, and the total number of falls during the hospital stay will be recorded.

Falls and dates of falls prior to hospitalization of less than 6 months will also be collected.

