4.5.7. Length of stay

The length of stay in days and hours in geriatric short-stay or post-emergency medicine, calculated between the start of hospitalization and the end of hospitalization, will be recorded.

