6.2.1. Description of planned statistical methods, including schedule of planned interim analyses

All variables will be described globally and by group. The description will include the number and percentage of modalities for qualitative variables, and the minimum, maximum, mean, standard deviation and median for quantitative variables.

All gait speed criteria, isochrony between imagined and executed gait speed, isochrony between normal gait speed and double-task gait will be compared using linear models taking into account the baseline J1 value.

As the evaluation conditions between D1' and D8 are different, the models evaluating evolution at D1' and D8 will be independent.

Fear of falling will be assessed using the Falls Efficacy Scale International questionnaire. Fear of falling is defined with a cut-off score equal to 10 on this questionnaire.

The number and percentage of patients with a fear of falling will be presented and compared at D1' and D8 using a Chi2 test.

Length of stay will be compared using a Student's t test.

The presence of falls and their consequences will be described during the hospital stay.

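### Falls are described only over each patient's own hospital stay, with no time at risk, so a difference in stay between arms would blur the by-arm comparison (minor)

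*Combined protocol and SAP*

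**What the plan says.** Section 2.2.2 defines the fifth secondary endpoint as "Presence of fall(s) and their consequences during hospitalization". The corresponding objective in 2.2.1 asks about the effect of socks on whether falls occur. Section 6.2.1 plans no test or estimate for it: "The presence of falls and their consequences will be described during the hospital stay". The same section has a general rule, "All variables will be described globally and by group", with counts and percentages for qualitative variables and the usual summary statistics for quantitative ones.

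The raw material for a rate is collected. Section 4.5.4 records "The occurrence of a fall during hospitalization, the time of the fall and its consequences, and the total number of falls during the hospital stay". Section 4.5.7 records "The length of stay in days and hours in geriatric short-stay or post-emergency medicine", counted from the start to the end of hospitalisation. No section combines the two or sets a fixed window for falls.

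Under 4.1.4 the allocated condition (socks or bare feet) is kept for the whole stay. Section 1.2.1 lists among the expected group benefits improved care "at a lower cost to society thanks to a shorter length of stay", and 1.1.2 anticipates a quicker return home. Length of stay is the sixth secondary endpoint, compared in 6.2.1 by a t test.

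**The concern.** A yes/no outcome counted over a period that varies between patients depends on both the daily risk and the length of the period. Here the period is the patient's own stay, which the intervention is hoped to shorten. If it does, fewer sock patients will have a recorded fall even when the risk on any given day is the same in both arms, and a somewhat higher daily risk could be offset. A sock effect on stay is not needed. With 25 per arm, and an assumed standard deviation of stay of 5 to 8 days, the standard error of the difference in mean stay is SD × √(2/25), or 1.4 to 2.3 days. Chance differences of a few days are therefore ordinary.

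Falls run through the rationale in section 1.1.1 and are the only specific harm among the endpoints, while 1.2.2 states that the socks add no risk. Readers will take the by-arm falls table as the trial's evidence on that statement, whether or not a test is attached.

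**Working it through.** **The plan's own figures.** The documents give no fall rate, expected stay or falls-related sample size, so there is no falls figure to reproduce. The sample size matters here only for the arm size. With a difference of 0.10 m/s, SD 0.10, two-sided 5% and 90% power (6.2.2; two-sided is assumed), a two-sample t test needs 22.02 per arm. That rounds up to 23 per arm and 46 in total, as stated. Fifty patients randomised 1:1 (6.2.8) gives about 25 per arm.

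**Assumptions (not in the documents).** A constant rate of 5, 10 or 15 falls per 1000 patient-days, and a stay of 15 v 12 days or 14 v 9 days (control v socks). For simplicity every patient in an arm has the same stay.

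**Formula.** P(at least one fall) = 1 − exp(−rate × stay). Expected fallers = 25 × P.

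**Same daily rate in both arms:**

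| Rate per 1000 days | Stay, days | % with a fall | Apparent risk ratio | Fallers of 25 | Difference |
|---|---|---|---|---|---|
| 5 | 15 v 12 | 7.2 v 5.8 | 0.81 | 1.81 v 1.46 | 0.35 |
| 10 | 15 v 12 | 13.9 v 11.3 | 0.81 | 3.48 v 2.83 | 0.66 |
| 15 | 15 v 12 | 20.1 v 16.5 | 0.82 | 5.04 v 4.12 | 0.92 |
| 5 | 14 v 9 | 6.8 v 4.4 | 0.65 | 1.69 v 1.10 | 0.59 |
| 10 | 14 v 9 | 13.1 v 8.6 | 0.66 | 3.27 v 2.15 | 1.11 |
| 15 | 14 v 9 | 18.9 v 12.6 | 0.67 | 4.74 v 3.16 | 1.58 |

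The true rate ratio is 1 in every row.

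**Offsetting case.** The two percentages are equal when the rate ratio (socks/control) equals control stay divided by sock stay. For 15 v 12 days this is 15/12 = 1.25: at a control rate of 10 per 1000, both arms show 13.9%. For 14 v 12 days it is 1.17, and for 14 v 9 days 1.56.

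**How much a rate can tell.** At 5 per 1000 with 15 v 12 days, expected falls are 25 × 15 × 0.005 = 1.875 and 25 × 12 × 0.005 = 1.5. Under a Poisson model, the chance that at least one arm has no falls is 1 − (1 − e^−1.875)(1 − e^−1.5) = 0.34. A rate corrects the scale but will be imprecise.

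**The case against.** The strongest reply is that the planned summary is not wrong. The objective concerns whether falls occur, and the share of patients who fall during their stay answers that, including any benefit from going home sooner. A daily rate answers a different question. This stands, and it is why the planned summary should be kept and supplemented.

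Second, the general rule in 6.2.1 means that number of falls and length of stay will both be described by arm, so an attentive reader could form a crude rate. This largely stands. However, the fall count lacks a denominator too, and the recorded stay starts at admission. Under 4.1.1 the physiotherapist first sees the prescription on the next working day, so the reader's ratio would include days before randomisation.

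Third, nothing is tested, so no false significant result can follow. The distortion is under one patient in four of the six rows above. If stay does not differ, there is no distortion from this source. All of this stands.

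A reader might also infer that patients who leave early, die or withdraw are scored as not having fallen. The documents do not say so. Section 4.7.2 stops data collection after withdrawal of consent, and 6.2.5 requires missing data and reasons to be described by group. The inclusion criterion in 3.2 of at least 7 days of physiotherapy should also make very short follow-up uncommon.

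**Conclusion.** The point holds as a minor one. Falls are summarised over follow-up that varies by patient and may vary by arm, with no time at risk and no common window. Under the assumed rates and stays, a stay shorter by 3 to 5 days gives an apparent risk ratio of 0.65 to 0.82 with no true effect, or about 0.35 to 1.6 fallers with 25 per arm. These figures depend on an assumed constant rate and on stay actually differing. The documents support the direction of the hoped-for change in stay but not its size.

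It is tempting to conclude that the plan will hide harm from the socks, or that presence over the stay is an invalid endpoint. The documents support neither. They give no evidence of a raised fall rate, length of stay will be reported alongside, and presence over the stay matches the stated objective. The risk is a misleading description, not a wrong test result.

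**What to change.** Keep the falls sentence in 6.2.1 and add, by arm:

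- (a) the number and percentage of patients with a fall between randomisation and D8, with the number still under observation at D8;
- (b) the number of falls after randomisation, the patient-days from randomisation to discharge, death or withdrawal, and falls per 1000 patient-days. Any rate ratio is descriptive, with an exact 95% confidence interval.

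State that days and falls before randomisation are excluded, because the stay in 4.5.7 starts at hospitalisation.

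The cost is a few lines of text and code. Fall times, fall counts and stay are already recorded, and no patient's care changes. The limits should be stated in the report: the D8 window leaves out later falls (covered by (b)), the rates will be imprecise, an arm with no falls is plausible, and repeat fallers can make a simple Poisson interval too narrow.

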6.2.2. Statistical justification of the number of inclusions

Walking speed is a common physiotherapy test used to assess motor function. It is easy to use, even for patients with cognitive and confusional disorders. Gait speed in patients over 80 years of age is $0.943\text{m/seconds} \pm 0.091$ (Bohannon & Williams Andrews, 2011; Menant et al., 2014)

According to Perera et al. an improvement in walking speed of 0.10m/s is considered clinically relevant (Perera et al., 2006).

For the purposes of this study, we therefore assume a difference of 0.10m/s between the 2 groups, and a standard deviation of 0.10 for the difference.

Based on these assumptions, and for an alpha risk of 5% and power of 90%, a total of 46 patients are required. To guarantee the power of the study, 50 patients will be randomized.

6.2.3. Expected statistical significance

The alpha risk is set at 5%.

6.2.4. Statistical criteria for discontinuing research

NA

6.2.5. Method for taking into account missing, unused or invalid data

All missing data and their reasons are described for each group.

For the primary endpoint, if data are missing at D8, they will be imputed by the patient's baseline value (D1).

If, for this criterion, more than 10% missing data are observed, a sensitivity analysis of the imputation method will be carried out: a multiple imputation method will be applied.

6.2.6. Managing changes to the initial strategy analysis plan

NA

6.2.7. Choosing the people to include in analyses

The main analysis will be carried out on the Intent-to-Treat (ITT) population, i.e. on all randomized patients.

A complementary analysis will be carried out on the Per Protocol (PP) population, including randomized patients for whom no major protocol deviations have been identified.

A data review meeting will be organized to review and define the major criterion or not for each deviation.

6.2.8. Randomization

Randomization will not be stratified

It will be carried out in a 1:1 ratio and in blocks.

Randomization will be carried out in Ennov Clinical by connecting to the website: <https://nantes-lrsy.hugo-online.fr/EnnovClinical/>. The connection will be made using a login, a password and a study number, issued by the data manager of the Research Unit of the CHD La Roche sur Yon. The following information must be entered:

- First initial of the name,
- First initial of the first name,
- Month and year of birth,

Compliance with inclusion and non-inclusion criteria (yes/no),

Randomization will be carried out by the physiotherapist or other authorized person after confirming the patient's inclusion in the study and obtaining oral consent. Randomization will be carried out prior to the D1 assessments. The inclusion number will be assigned automatically during randomization. An e-mail confirmation will be sent to the person who carried out the randomization, and to all those concerned.

The randomization list will be drawn up by the biometrics team at the CHD La Roche sur Yon Research Unit. An explanatory guide to randomization will be available online at Ennov Clinical.

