2.1.2. Primary endpoint

Evolution of walking speed at the patient's preferred speed over 10m between D1 (start of physiotherapy treatment) and D8. Two tests will be performed at each assessment, and the average of the two tests will be used.

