4. DESIGN AND STUDY PROCESS

4.1. Study schedule

4.1.1. Inclusion and baseline tests (J1)

Patients arrive on the ward and are assessed by the doctor, who prescribes physiotherapy if necessary.

The physiotherapist takes note of the prescription on the first working day thereafter. The physiotherapist carries out a routine analysis of the patient's footwear. If the footwear is unsuitable, or if the patient is barefoot, the physiotherapist checks the patient's eligibility criteria. If the patient meets these criteria, he or she is informed of the study. If the patient gives oral consent, the physiotherapist will perform the Baseline tests (D1).

Baseline: J1 tests

The physiotherapist assesses the patient during the first diagnostic session, and performs the *Confusion Assessment Method* if it has not been done in routine practice.

A Visual Analogue Fatigue Assessment will be carried out prior to clinical testing.

For research purposes, the J1 tests will be performed barefoot:

1. Patient's walking speed over 10 m (2 times)
2. Walking speed in dual-task situation over 10 m (2 times)

Two other less common but validated assessments in this population will be carried out.

3. Imagined walking speed over 10 m (2 times)

The average of each of the two tests will be used for items 1 to 4.

Together, these tests take the patient around 10 minutes.

4. Short-Falls Efficacy Scale International Questionnaire

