4.1.2. Randomization

Once the tests have been carried out, randomization will be carried out by the physiotherapist.

Randomization arm :

- Control arm: usual care with bare feet.
- Experimental arm: specific management with non-slip socks.

Depending on the randomization arm, the physiotherapist will put non-slip socks on patients in the experimental arm and leave patients in the control arm barefoot. He will then encourage the patient to walk for 3 minutes.

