4.1.3. J1' follow-up

After these 3 minutes of walking with or without the socks, depending on the randomization arm, and in order to assess the immediate effect of wearing anti-slip socks on motor skills, the patient will perform the same tests as on D1, in the same order.

A Visual Analogue Fatigue Assessment will be performed prior to the following clinical tests:

1. Patient's walking speed over 10 m (2 times)
2. Walking speed in dual-task situation over 10 m (2 times)
3. Imagined walking speed over 10 m (2 times)

The tests will be carried out by the patient with bare feet (control arm) or with non-slip socks (experimental arm).

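### Sections 4.1.2 and 6.2.8 give opposite orders for randomisation and the D1 tests; following 6.2.8 would put the primary baseline after allocation in an open study

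*Combined protocol and SAP*

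**What the plan says.** On the order of events:

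- Section 4.1.1 goes from oral consent directly to the D1 tests, which are done barefoot, with no randomisation step in between.
- Section 4.1.2: "Once the tests have been carried out, randomization will be carried out by the physiotherapist". Socks are then put on, or the patient stays barefoot, for a 3-minute walk.
- Section 4.1.3 places the D1' tests next: "After these 3 minutes of walking with or without the socks, depending on the randomization arm".
- Section 6.2.8, which describes the online randomisation procedure: "Randomization will be carried out prior to the D1 assessments".

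On the use of D1:

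- Section 2.1.2 defines the primary endpoint as the change in preferred 10 m walking speed "between D1 (start of physiotherapy treatment) and D8".
- Section 6.2.1 says the gait speed criteria "will be compared using linear models taking into account the baseline J1 value".
- Section 6.2.5 replaces a missing D8 value of the primary endpoint with the patient's D1 value.
- Section 6.2.7 runs the main analysis by intention to treat, "i.e. on all randomized patients".

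Section 4.2 describes the study as open. The physiotherapist does the D1 tests (4.1.1) and is named as the person who randomises (4.1.2 and 6.2.8, the latter also allowing another authorised person). No blinded assessor is described.

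**The concern.** Staff cannot obey both instructions, and the choice between them decides whether the primary baseline is a pre-allocation or a post-allocation measurement.

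Adjusting for a baseline is safe because, when measured before allocation, it cannot depend on the arm. Under the 6.2.8 order that guarantee is lost. Patient and tester could both know the arm during a preferred-speed walk, where expectation or encouragement may matter. Any resulting difference at D1 would be treated as a true difference in starting level and adjusted away, which displaces the estimated effect at D8.

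There is a second, smaller consequence. A patient who proves unable to do a test at D1 would already be in the ITT set without that baseline, and section 6.2.5 gives an imputation rule only for a missing D8 on the primary endpoint. For the 10 m walk this should be uncommon, because section 3.2 requires the ability to walk 10 m. It is more plausible for the dual-task or imagined walk, which are secondary.

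**Working it through.** **Reading the sections together.** Sections 4.1.1 to 4.1.3 give: consent, D1 tests, randomisation, 3-minute walk, D1' tests. Section 2.2.2 agrees, since it defines D1' by footwear assigned at randomisation. Section 6.2.8 gives: consent, randomisation, D1 tests. The schedule table in 4.1.5 does not settle the matter: randomisation and the tests share the J1 column, and row order need not mean timing. The two orders cannot be reconciled as written.

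**The plan's own figure.** Section 6.2.2 assumes a difference of 0.10 m/s, SD 0.10, alpha 5% and power 90%, and states 46 patients. The two-sided t-test calculation gives 22.02 per arm, rounded up to 23, so 2 × 23 = 46. The figure reproduces and does not depend on the order of randomisation.

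**Size of the possible bias.** The documents supply neither the D1 shift nor the slope of D8 on D1, so both are assumptions here. Let b be the shift in one arm's D1 speed caused by knowing the arm, s the slope, and suppose no true effect. The D8 means are then equal, the observed D1 means differ by b, and the adjusted difference is

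bias = 0 − s × b = −s × b.

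If the sock arm's D1 is too slow (b negative), the sock effect is inflated; if too fast, it is reduced. Absolute values, in m/s:

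| b | s = 0.5 | s = 0.7 | s = 0.9 |
|---|---|---|---|
| 0 | 0 | 0 | 0 |
| 0.02 | 0.010 | 0.014 | 0.018 |
| 0.05 | 0.025 | 0.035 | 0.045 |

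Against the design difference of 0.10 m/s, these are 10% to 18% for b = 0.02 and 25% to 45% for b = 0.05.

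**Simulation check.** This used 25 patients per arm, no true effect, 4,000 trials per setting, a D1–D8 correlation equal to s, and the SD of 0.10 read as the SD of the change. Mean biases were 0.0101, 0.0143 and 0.0185 for b = 0.02, and 0.0249, 0.0353 and 0.0445 for b = 0.05. The two-sided type I error, nominally 5%, was about 7%, 8% and 10% for b = 0.02, and 16%, 25% and 34% for b = 0.05.

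**Effect of the imputation rule.** If a fraction m of D8 values is replaced by D1, the D8 means differ by m × b and the slope becomes (1 − m) × s + m. Then

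bias = m × b − [(1 − m) × s + m] × b = −(1 − m) × s × b.

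With m = 0.10 each entry is 10% smaller; for example 0.014 becomes 0.0126 and 0.035 becomes 0.0315 m/s. The imputation rule therefore does not add to this bias.

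**How large these shifts are in seconds.** At the protocol's 0.943 m/s, 10 m takes 10/0.943 = 10.60 s.

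- A shift of 0.02 m/s: 10/0.923 − 10/0.943 = 0.23 s slower, or 10/0.943 − 10/0.963 = 0.22 s faster.
- A shift of 0.05 m/s: 10/0.893 − 10/0.943 = 0.59 s slower, or 10/0.943 − 10/0.993 = 0.53 s faster.

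**The case against.** The strongest reply is that 6.2.8 is a slip for D1'. Randomising before the D1' assessments would agree with every other section, and the labels D1 and D1' are used loosely elsewhere: the Short-FES-I is listed at D1' in 2.2.2 and 4.6 but not in 4.1.3 or the schedule. This is plausible, but it remains inference. The sentence says D1 and stands in the section that governs the randomisation procedure, so staff could well act on it. If it is a slip, correcting it is all the more straightforward.

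Second, D1 is barefoot in both arms, so the allocated footwear cannot alter it. That is true and it narrows the route to knowledge of the arm. The scripted instruction and the averaging of two trials may limit that route further, but they do not close it.

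Third, section 3.3 already excludes patients unable to do the study tests, and 6.2.8 requires eligibility to be declared at randomisation. This partly answers the point about missing baselines. Under the 6.2.8 order, however, the declaration comes before the tests have been tried.

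Fourth, the bias figures rest wholly on assumed shifts and slopes. That stands: they show scale and are not evidence that a shift would occur.

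Finally, D8 is assessed openly in any case. That also stands, and correcting 6.2.8 does not remove it. It is no reason to add a second, avoidable weakness at baseline.

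**Conclusion.** The contradiction is certain: two current sections give opposite orders and nothing in the document resolves them. The bias is conditional. It requires that 6.2.8 is followed and that knowing the arm changes D1 speed; if either fails, it is zero. Its size and direction cannot be determined from the documents. Under assumed shifts of 0.02 to 0.05 m/s and slopes of 0.5 to 0.9, the baseline-adjusted effect would be off by 0.010 to 0.045 m/s against a design difference of 0.10 m/s. The correction is needed because the conflict concerns allocation and the primary baseline, and a baseline taken after allocation cannot be remeasured once the patient has been tested.

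**What to change.** Replace the sentence in section 6.2.8 with: *Randomization is carried out after the D1 barefoot tests and the Short-FES-I are completed and recorded on the source document, and before the 3-minute walk and the D1' tests.* Put the same order in the online randomisation guide. It would also help to record the times of D1 completion and of randomisation, so that the order can be verified for each patient.

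This matches 4.1.2 and is workable with the procedure described. Section 4.6 already lists the D1 walk durations as source data, and the randomisation entry fields in 6.2.8 include no D1 values.

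The cost is one protocol sentence and the matching text in the guide, with no extra patients or visits. There are two minor consequences. If the sponsor wants D1 entered in the eCRF before allocation, the inclusion number would have to be issued earlier than 6.2.8 provides. In addition, a few patients may consent and be tested but not be randomised; the list in section 3.3 covers only those who fail eligibility, so these patients should be logged as well.
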